8.1.3 MRD Evaluations

8.1.3.1 MRD Evaluations by MCF

The primary end-point analysis will be performed by the Department of Pathology at the University of Chicago. Bone marrow aspirate for MRD analysis by 10-color multiparameter flow cytometry will be collected for all patients at the time of enrollment and during all subsequent bone marrow biopsies, including at the end of treatment (a minimum of two samples per patient). All samples collected at participating sites will be shipped and processed at the University of Chicago laboratories. Instructions detailing the collection method, processing, and shipment of these samples will be provided in a separate manual.

8.1.3.2 MRD Evaluations by gene sequencing

8.1.4As part of an additional MRD evaluation, all bone marrow aspirates collected for MRD analysis will also be analyzed using the. Clono SEQ® platform. The collection time points will be as described above: at the time of enrollment, at any time during a suspected CR or better, and at 12 months/end of treatment. The samples will be part of the same aspirate collected for multiparameter flow cytometry and the details of this collection will be described in a separate manual. All samples will be sent to the University of Chicago Multiple Myeloma Program Coordinator. Processing of samples including DNA isolation, storage, and shipment to Adaptive Biotechnologies will be performed by the University of Chicago laboratory. Samples processing at the University of Chicago will be supported by separate grants and funds from the University of Chicago investigators. Adaptive Biotechnologies will provide funding for Clono SEQ® analysis. **Populations for Analysis**

The Intent-to Treat (ITT) population of patients will be defined as all patients who receive at least one dose of treatment in either of the arms (ixazomib or lenalidomide or dexamethasone in the experimental arm or lenalidomide in the control arm). “A secondary, evaluable population will also be analyzed that will include all patients in the ITT population with the following exceptions:

- (1) Patients who discontinued the trial for reasons other than toxicity or progressive disease, and
- (2) Patients who met eligibility for MRD positive disease but the MRD testing at the 12-month timepoint is either not successful (by NGS) or the sample is not available (pt withdraws consent, sample is a dry tap, etc).

Patients in categories (1) or (2) will be rendered “non-evaluable.” Additionally, in the situation that a patient is rendered non-evaluable, a new patient will be randomized into the trial to preserve the sample size for primary endpoint analysis. Additionally, in the situation that a

patient is rendered non-evaluable, a new patient will be randomized into the trial to preserve the sample size for primary endpoint analysis. Patients enrolled in this trial will be patients who completed initial induction followed by autologous stem cell transplant for symptomatic myeloma (per IMWG criteria) and in the first 0-6 months of Lenalidomide maintenance provided that was initiated within 6 months after transplant as per standard of care and with at least MRD-positive residual myeloma. The study's primary endpoint, attainment of MRD-negative disease by MFC will be assessed at the completion of the 12 cycle of protocol treatment (both arms). In patients that were enrolled based on their MRD-positivity by MFC, an improvement will be counted when these patients switch to MRD-negative disease by MFC at the 12-month time-point. Patients that were enrolled per their MRD-positivity by NGS will require NGS analysis to determine their MRD status at 12 months of treatment. In this patient population, only a switch from MRD-positivity to negativity by NGS will be counted as an improvement. We anticipate that no more than 10% of patients will be enrolled who are MFC negative but NGS positive. If there is an imbalance between the two treatment arms in this variable we will adjust by post-hoc stratification or covariate analysis. All patients enrolled and receiving any IRD or R treatment will be evaluable for this endpoint, with the exception of patients that decline to receive treatment for reasons unrelated to toxicity and/or efficacy. Patients in that category will be replaced. All other patients who discontinue treatment before receiving 12 cycles of protocol treatment will be considered treatment failures for assessment of the study's primary endpoint. The proportion of MRD-negative patients will be reported along with 95% confidence intervals.

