4.3 Number of Patients

A total of 60 patients will be enrolled in a 1:1 ratio into one of two arms: IRd or lenalidomide alone. Enrollment is defined as the time of randomization. **Protocol treatment must start within 2 days of randomization.**

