6. REGISTRATION PROCESS

When a potential patient has been identified, notify the CRA via phone or email to ensure a reservation on the study (contact information listed on enrollment form). Reservations for potential subjects will only be held for subjects who have signed consent for that particular study.

When registering a subject, the following must occur:

- Confirm that the institution has a current IRB approval letter for the correct version of protocol/consent and has an annual update on file, if appropriate.
- Submit all required materials (Eligibility Checklist, Source documentation, & signed consent form) to confirm eligibility and required pre-study procedures to the CRA a minimum of 48 hours prior to the subject's scheduled therapy start date.
- Source documentation includes copies of all original documents that support each inclusion/exclusion criteria. The eligibility checklist does not serve as source documentation but rather as a checklist that original source documentation exists for each criterion.
- Communicate with the CRA to ensure all necessary supporting source documents are received and the potential subject is eligible to start treatment on schedule. If there are questions about eligibility, the CRA will discuss it with the PI. PI may clarify, but not overturn, eligibility criteria.
- Affiliate sites must confirm registration of subjects by obtaining a subject study ID number from the CRA via phone, fax or email.
- If a subject does not start on the scheduled day 1 treatment date, promptly inform the CRA as the delay in start may deem the subject ineligible and/or require further or repeat testing to ensure eligibility.
- The date the patient is randomized if randomization is involved or receives treatment for the first time will be considered the patient's "On Study Date." The patient's subject ID will be assigned and a confirmation of registration will be issued by the CRA on this date. Subjects that sign consent and do not go "On Study" will be recorded in the database with the date they signed consent and the reason for not going "On Study" (e.g., Ineligible, Screen Failure or Withdrawn Consent).

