10.3 Adverse Event Reporting Procedures

Information about all AEs, whether volunteered by the subject, discovered by investigator questioning, or detected through physical examination, laboratory tests or other means, will be collected and recorded and followed as appropriate.

All AEs (e.g., any new event or worsening in severity or frequency of a pre-existing condition or laboratory finding) with an onset date on or after the first dose of treatment through 30-days after the last treatment dose must be promptly documented on the appropriate CRF in eVelos. Any SAE (Section 10.4) which is considered related to study procedures and occurs after informed consent but before Cycle 1 Day 1 must be reported. Details of the event must include severity, relationship to study drug, duration, action taken, and outcome. All AEs must be followed to resolution or stabilization regardless of relationship to study drug.

All AEs that are considered related to study drug must be followed to resolution or stabilization if improvement is not expected.

AEs must be reported from the date of the first dose of treatment through 30 days post-last dose of study treatment or initiation of a new anti-cancer therapy, whichever occurs first. If a subject is enrolled but discontinues study prior to receiving any study drug, only SAEs that are considered related to study procedures must be reported through the end-of-study visit. AEs which completely resolve and then recur should be recorded as a new AE. For subjects who complete the end of study visit less than 30 days following their last dose of study drug, a follow up of ongoing AEs should be attempted by telephone, and documented in the subject's source.

AEs continuing at 30 days post-last dose should have a comment in the source by the Treating Investigator that the event has stabilized or is not expected to improve. SAEs continuing at 30 days post-last dose should be followed until resolution or stabilization.

Whenever possible, the Common Terminology Criteria for Adverse Events (CTCAE) version 4.0 should be used to describe the event and for assessing the severity of AEs. Any events representing a change in the CTCAE Grade need to be reported on the AE case report form. This includes any change in laboratory values.

For AEs not adequately addressed in the CTCAE, the severity table below may be used:

Severity	Description

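### The set called ITT in Section 8.1.4 requires a first dose, so a patient randomised but never dosed leaves both efficacy sets after the arm is known

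*Combined protocol and SAP*

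**What the plan says.** - Section 8.1.4, Populations for Analysis (its heading is run into the text of 8.1.3.2), has an ITT population "defined as all patients who receive at least one dose of treatment in either of the arms". A secondary evaluable population is carved out of that set, so it is also limited to dosed patients.
- The same section says of the primary endpoint: "All patients enrolled and receiving any IRD or R treatment will be evaluable for this endpoint". It excepts "patients that decline to receive treatment for reasons unrelated to toxicity and/or efficacy. Patients in that category will be replaced".
- The failure rule follows: "All other patients who discontinue treatment before receiving 12 cycles of protocol treatment will be considered treatment failures".
- Section 4.3: "Enrollment is defined as the time of randomization" and "Protocol treatment must start within 2 days of randomization".
- Section 4.1 describes an open-label trial with 1:1 allocation.
- Section 10.3 sets safety reporting for a case that 8.1.4 does not address: "If a subject is enrolled but discontinues study prior to receiving any study drug".
- Section 8.1.6 states the primary comparison (one-sided 10%; chi-square or Fisher, and a stratified CMH test) but names no analysis population.

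**The concern.** An intention-to-treat set keeps everyone who was randomised, so that nothing after allocation can decide who is compared. Here membership depends on a later event, the first dose, and in an open-label trial that event can depend on the arm. The arms differ in burden. Control is lenalidomide 10 or 15 mg. The experimental arm starts with lenalidomide 25 mg plus weekly ixazomib and dexamethasone 40 mg. A patient who hears the allocation and does not start may differ in prognosis from one who does.

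At stake is the randomised basis of a decision that rests on few events. At the planning rates the expected counts are 30 × 0.267 = 8.0 v 30 × 0.05 = 1.5 MRD-negative patients.

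**Working it through.** **1. Following one patient through the text.** The patient is randomised, hence enrolled (4.3), and the arm is known (4.1). No dose is taken, which 10.3 foresees. The patient is then outside the ITT set, outside the evaluable set nested in it, and not evaluable under the primary-endpoint sentence. The failure rule speaks of patients who discontinue treatment and comes after a sentence confined to treated patients, so it does not clearly bring this patient back. No efficacy set of all randomised patients is defined.

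**2. The plan's own figure.** Inputs from 8.1.1 and Table 8-1: 30 per arm, one-sided α = 0.10, 80% power. Exact Fisher power is the sum of P(x)P(y) over binomial outcomes with p ≤ 0.10. It is 79.9%, 80.0%, 80.1%, 80.1% and 80.0% for the five rows, so the table reproduces. The test named there, CMH with continuity correction, gives 77.2% at 26.7% v 5% when computed exactly without strata.

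**3. How often the verdict would depend on the rule.** Assumption: k = 1, 2 or 3 never-dosed patients in one arm, no replacement, dosed patients at 26.7% v 5%. The probability is the sum of P(x)P(y) over outcomes where the decision with 30 per arm (never-dosed counted as failures) differs from the decision with those k removed.

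| k | Fisher, IRd | Fisher, control | Uncorrected chi-square, IRd | Uncorrected chi-square, control |
|---|---|---|---|---|
| 1 | 0.62% | 4.79% | 0.17% | 0.67% |
| 2 | 0.72% | 4.73% | 2.91% | 2.39% |
| 3 | 5.42% | 4.72% | 3.22% | 2.31% |

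Over all rows of Table 8-1 the maximum is 9.5% (Fisher) and 7.4% (chi-square), both at 48.1% v 20% with three in IRd. Removing failures raises the observed rate of the arm that they leave. So changes in the IRd columns all favour IRd, and those in the control columns all go against it.

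**4. Worked outcomes (one-sided Fisher).**
- 6/30 v 2/30: p = 0.127, not significant. With 1, 2 or 3 IRd failures removed: 6/29 gives 0.116, 6/28 gives 0.106, and 6/27 gives 0.095, which is significant.
- 8/30 v 2/30: p = 0.040. 8/27 v 2/30 gives 0.026 and 8/30 v 2/27 gives 0.057, so the verdict does not change.

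**5. Power of the two analyses (Fisher, 26.7% v 5%).**

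| Never-dosed | Dosed-only | All randomised, never-dosed as failures |
|---|---|---|
| 1 per arm of 30 | 78.6% | 78.6% |
| 3 per arm of 30 | 75.4% | 75.4% |
| 1 or 3 per arm, replaced so that 30 are dosed | 80.0% | 80.0% |

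The fall from 80.0% comes from having fewer dosed patients, and both analyses share it. If the never-dosed patients are all in one arm, the analyses differ by the step 3 amounts. With three in IRd only, dosed-only power is 78.0% and all-randomised power is 78.0 − 5.4 = 72.6%. With never-dosed patients in control only, the all-randomised analysis has the higher power.

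**The case against.** The other side is fair on several points. This is a proof-of-concept phase II, where a dosed population is common. Dosed patients who stop early already count as failures, apart from the excepted group. The 2-day limit in 4.3 leaves little time for a patient to drop out once the arm is known. The number never dosed is unknown and may be zero. If non-start is unrelated to outcome, Fisher type I error in the dosed-only sets stays below 10% (1.5-5.9% with one or three removed from one arm and true rates of 5-20%). All of this limits the size of the problem. None of it supplies a rule for the patient whom 10.3 foresees, or makes the ITT label correct.

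Four stronger readings are tempting but not supported:
- *The clause on declining treatment removes never-dosed patients.* It is written as an exception to the treated group, so it may describe withdrawal after dosing. The text does not settle this. The dose requirement excludes never-dosed patients either way.
- *Section 6 removes randomised patients who start late.* It tells sites to "promptly inform the CRA as the delay in start may deem the subject ineligible and/or require further or repeat testing to ensure eligibility". That sits in a list about registering a subject, which also covers consented patients who never go on study. The ineligibility may fall before randomisation.
- *The day windows in 8.1.2 leave patients undosed.* They fit imperfectly with 4.3 and 5.1, but randomisation from Day +78 satisfies both 8.1.2 and 4.3. A clash of dates does not show that anyone goes without treatment. It is a separate consistency point.
- *The stated power is wrong, or the result is biased towards IRd.* Table 8-1 reproduces, and the documents give no basis for a direction.

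**Conclusion.** The point holds as a gap in the definition of the analysis population. Following 8.1.4 as written, a patient randomised and never dosed leaves both efficacy sets after the arm is known. One step is inference: 8.1.6 names no population, so use of the dosed set for the primary test is read from 8.1.4, whose evaluability sentence supports that reading directly.

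The size and direction of any bias cannot be derived from the plan. The 0.6-5.4% and 4.7-4.8% figures rest on an assumed 1 to 3 never-dosed patients in one arm, the planning rates, and Fisher's test. They measure how often the counting rule decides the verdict; they do not estimate bias. The change is worth making because it removes the question at little cost.

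**What to change.** In 8.1.4, define ITT as all randomised patients analysed in the assigned arm. Count a never-dosed patient as not MRD-negative, in line with the failure rule already there. If a replacement is randomised, keep the original patient in the analysis. Rename the dosed set modified ITT or safety set. In 8.1.6, name the all-randomised set as the population for the primary MRD comparison. Keep the 2-day start limit in 4.3, since a longer one would give more time for drop-out after allocation.

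The change is to the wording of the analysis sections. Its cost is slight dilution of the observed rates. With one never-dosed of 30 per arm, 26.7% × 29/30 = 25.8% and 5% × 29/30 = 4.8%; with three, 26.7% × 27/30 = 24.0% and 5% × 27/30 = 4.5%. With equal numbers per arm, power is the same as for the dosed-only analysis at the planning rates. It is lower only if non-start is concentrated in IRd, which is where dropping those patients would favour the experimental arm.

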- 27) Acute infection requiring systemic anti-infectives, antivirals, or antifungals within two weeks prior to first dose
- 28) Systemic treatment, within 14 days before the first dose of ixazomib, with strong CYP3A inducers (rifampin, rifapentine, rifabutin, carbamazepine, phenytoin, phenobarbital), or use of Ginkgo biloba or St. John's wort.
- 29) Ongoing or active systemic infection, active hepatitis B or C virus infection, or known human immunodeficiency virus (HIV) positive.
- 30) Any serious medical or psychiatric illness that could, in the investigator's opinion, potentially interfere with the completion of treatment according to this protocol.
- 31) Known allergy to any of the study medications, their analogues, or excipients in the various formulations of any agent.

32) Known GI disease or GI procedure that could interfere with the oral absorption or tolerance of ixazomib including difficulty swallowing.
33) Diagnosed or treated for another malignancy within 2 years before study enrollment or previously diagnosed with another malignancy and have any evidence of residual disease. Patients with non-melanoma skin cancer or carcinoma in situ of any type are not excluded if they have undergone complete resection.
34) Patient has \geq Grade 3 peripheral neuropathy or Grade 2 with pain on clinical examination during the screening period.
35) Participation in other clinical trials, with other investigational agents not included in this trial, within 30 days of the start of this trial and throughout the duration of this trial.

Duration of Study:

Subjects will be treated on protocol for 12 months or until disease progression or if lenalidomide and/or ixazomib are permanently discontinued due to intolerance before the end of 1 year. Patients who complete 12 months of protocol treatment will be taken off protocol with management as per PI discretion and standards of care but will continue to be followed for progression, if the patient did not progress on study treatment, and survival.

STUDY OVERVIEW DIAGRAM

SCHEDULE OF EVENTS

Assessment	Screening ²	Cycles 1-12				EOT	Long-term follow-up
		1	8	15	22		
Day	-42 to -1						
Informed Consent+♥	X						
Medical History / Treatment History ¹	X						
Skeletal Survey	X						
ECG ³	X					X	
Physical Exam / ECOG ^{4,5}	X	X				X	
Vital Signs ⁶	X	X				X	
Height ⁷ , Weight, BSA	X	X				X	
24-hour urine ⁸	X	X				X	
Urinalysis	X					X	
C- Reactive Protein	X						
Hematology ⁹	X	X	[X]	[X]		X	

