19) All patients are required to have a sample for MRD collected at screening, at the End of Treatment visit, and at any other time a Bone Marrow biopsy/aspirate is collected as SOC. Additionally, FFPE or BMA slides from diagnosis will be required for calibration of MRD by NGS for all patients. If CR is recorded between screening and EOT, a Bone Marrow Biopsy can be indicated. However, if CR is suspected within 3 months of EOT, it is acceptable to wait for the EOT BM biopsy. It is expected that samples will be collected at a minimum of two time-points for each patient. Refer to lab manual for collection and shipping instructions. Central analysis includes MRD by multi-parameter flow cytometry and MRD by gene sequencing.							
20) AEs will be collected from the time of signing informed consent to 30 days following the last dose of treatment. Please refer to section 9 for specific collection requirements.							
21) Assessment for disease progression in subjects who did not progress during treatment. At least every 3 months (+/- 30 days) for 2 years from safety follow-up visit (which must be 28days (+/- 3 days) post-last study treatment).							
22) lenalidomide must be prescribed through and in compliance with the lenalidomide REMSTM program of Celgene Corporation. Prescriptions must be filled within 7 days. Consideration should be given to prescribing lenalidomide 5 to 7 days in advance of Day 1 of each cycle to allow time for required patient and prescriber surveys, and drug shipment to patient. Any unused lenalidomide will be counted and documented by each site.							
23) Control Arm: Lenalidomide should continue at best tolerated dose of either 10 mg or 15 mg on days 1-28. If the 10 mg dose is tolerated for three cycles, it can be escalated to 15 mg per dose.							

Assessment	Screening ²	Cycles 1-12				EOT	Long-term follow-up
		1	8	15	22		
Day	-42 to -1						
24) Experimental Arm: lenalidomide dosing Days 1-21. Cycle 1-4 lenalidomide will be administered at 25 mg daily. Cycles 5-12 lenalidomide will continue at best tolerated dose days 1-21. lenalidomide should be taken in the evening at approximately the same time each day.							
25) Cycles 1-4: Ixazomib at 3-4 mg Days 1, 8, 15. Cycles 5+ Ixazomib at best tolerated dose on Days 1, 8, 15. Ixazomib should be taken on an empty stomach or at least 1 hour before or 2 hours after a meal.							

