4.2.3 End of Treatment Procedures

Patients who discontinue therapy for any reason must have an end of treatment (EOT) visit completed 30 days (\pm 7 days) after the last application of study drug. Following the end of treatment, subjects will be followed for survival for 2 years.

Physical examination and vital signs	
• Body weight• Blood pressure, pulse, temperature• Physical examination• Pulse oximetry
Cardiac evaluation	12-lead ECG
Urinalysis	Urine bilirubin, glucose, hemoglobin, ketones, pH, protein
Hematology	Hemoglobin, hematocrit, mean corpuscular volume, mean corpuscular hemoglobin, mean corpuscular hemoglobin concentration, white blood cell (WBC) count, WBC differential, red blood cell count, lymphocytes, monocytes, neutrophils, band neutrophils, eosinophils, basophils, platelets. WBC differential may be automated or manual as per institutional standards. Reticulocytes may be done only when clinically indicated
Clinical chemistry	Sodium, potassium, chloride, bicarbonate, BUN, creatinine, glucose, calcium, phosphate, magnesium, ALT, AST, alkaline phosphatase, total bilirubin, total protein, albumin, uric acid, LDH, CRP

Pregnancy test (if applicable)	A serum pregnancy test will be performed in pre-menopausal women and women who are post-menopausal for < 2 years to exclude that a pregnancy occurred under treatment and in accordance with lenalidomide REMS™ (Appendix 13.6)
Myeloma Disease Assessment-laboratory	M-protein determination: 
• Serum Protein Electrophoresis (SPEP) and immunofixation• Urine Protein Electrophoresis (UPEP) and immunofixation• Serum Free Light Chains• Serum quantitative immunoglobulins (Igs)
Bone Marrow Biopsy	Quantify percent myeloma cell involvement, and obtain bone marrow aspirate for conventional cytogenetics and fluorescent in situ hybridization. A sample for MRD evaluation is required to be collected. For subjects who sign consent for correlative samples, an additional aspirate sample should be collected at screening (Section 8)
Correlative Samples	For patients who give consent, peripheral blood and bone marrow aspirate samples collected at End of Treatment
Neurotoxicity Assessment	Including Neurotoxicity Questionnaire (Appendix 5)
QOL Assessment	Patient reported survey
Adverse events	Record through 30-days after last treatment. All SAEs considered related to treatment must be followed until resolution.

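### Section 8.1.4 has conflicting evaluability and replacement rules for a patient who stops early for toxicity or progression and has no 12-month MRD sample

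*Combined protocol and SAP*

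**What the plan says.** The rules are in Section 8.1.4, Populations for Analysis (its heading is run into the end of Section 8.1.3.2).

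**Populations and exceptions.** The intent-to-treat (ITT) population is every patient who receives at least one dose. A secondary evaluable population removes two groups:
- Exception (1): "Patients who discontinued the trial for reasons other than toxicity or progressive disease". Toxicity and progression stoppers therefore stay in.
- Exception (2): patients who met MRD-positive eligibility but for whom "the MRD testing at the 12-month timepoint is either not successful (by NGS) or the sample is not available". The examples are withdrawn consent and a dry tap, and the list is left open.

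Either exception makes the patient non-evaluable, and then "a new patient will be randomized into the trial to preserve the sample size for primary endpoint analysis".

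**Failure rule, later in the same section.** "All patients enrolled and receiving any IRD or R treatment will be evaluable for this endpoint", except those who decline treatment for reasons unrelated to toxicity or efficacy; that group is replaced. "All other patients who discontinue treatment before receiving 12 cycles of protocol treatment will be considered treatment failures" for the primary endpoint.

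**When treatment ends early.** The Protocol Summary (Duration of Study) treats patients for 12 months, "until disease progression or if lenalidomide and/or ixazomib are permanently discontinued due to intolerance before the end of 1 year".

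**What sample then exists.** Section 4.2.3: "Patients who discontinue therapy for any reason must have an end of treatment (EOT) visit completed 30 days" (plus or minus 7) after the last dose. Schedule of Events footnote: "All patients are required to have a sample for MRD collected at screening, at the End of Treatment visit, and at any other time" a standard-of-care marrow is taken. Section 2.1 sets the primary endpoint at 12 months after randomization. Section 8.1.3.2 runs 12 months and end of treatment (EOT) together as one sampling point.

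**Primary test.** Section 8.1.6 names the tests and the 10% one-sided level, but no population.

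**The concern.** Take a patient who stops for intolerance at cycle 5. The failure rule makes this patient an evaluable failure who is not replaced. The only marrow the protocol then requires is the EOT marrow, about 30 days after the last dose. If that is not the 12-month sample, exception (2) read literally makes the same patient non-evaluable and brings in a replacement. The same holds for a patient who progresses. No sentence says which rule prevails.

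The literal reading would take out patients who failed treatment and move the result toward a rate among completers. Controls can stop too. But in the experimental arm (IRd) permanent discontinuation of either of two drugs can end protocol treatment, and lenalidomide starts at 25 mg (Section 7.2.1) against 10 or 15 mg in controls (Section 7.2.2). Removal that favours IRd is therefore plausible, although the documents give no stop rate. The trial is open-label (Section 4.1), so each decision on evaluability and replacement would be made with the arm known.

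**Working it through.** **Inputs.** 30 per arm and one-sided alpha 0.10 (Section 8.1.1); 5% against 26.7% (Table 8-1); Fisher's exact test, one of the tests in Section 8.1.6. Numbers of stoppers are assumptions.

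**The plan's figure.** Exact enumeration of one-sided Fisher with 30 per arm gives power 0.799, 0.800, 0.801, 0.801 and 0.800 for the five rows of Table 8-1. The stated 80% reproduces, so the sample size is not at issue. (A single-stratum Cochran-Mantel-Haenszel test with continuity correction gives 0.772 at 5% vs 26.7%.)

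**Model.** Let m IRd and k control patients stop early. Take 26.7% and 5% as net rates, that is, with stoppers counted as failures among 30. The rates among completers are then

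- q_E = 0.267 × 30/(30 − m): 0.297, 0.334, 0.381 for m = 3, 6, 9
- q_C = 0.05 × 30/(30 − k): 0.050, 0.052, 0.056 for k = 0, 1, 3

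Each stopper is replaced, and replacements are assumed to complete. Successes are S_E ~ Bin(30, q_E) and S_C ~ Bin(30, q_C) under both rules. Only the denominators differ:

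- stoppers dropped: S_E/30 against S_C/30
- stoppers kept as failures: S_E/(30 + m) against S_C/(30 + k)

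Both use the same enrolled patients, so the contrast isolates the scoring. Summing the joint probabilities over all outcomes:

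| Stoppers IRd/control | Power, kept | Power, dropped | Verdict differs |
|---|---|---|---|
| 3/0 | 0.83 | 0.87 | 3.8% |
| 6/0 | 0.85 | 0.92 | 7.3% |
| 9/0 | 0.91 | 0.97 | 5.7% |
| 3/1 | 0.82 | 0.86 | 3.7% |
| 6/3 | 0.88 | 0.91 | 2.8% |
| 9/3 | 0.91 | 0.96 | 5.2% |

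In every scenario the change is from not significant to significant. The percentages do not rise steadily because Fisher's test is discrete and power nears its ceiling.

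**Equal net rates in both arms: probability of a significant result.**

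| Net rate | Stoppers | Kept | Dropped |
|---|---|---|---|
| 5% | 6/0 | 2.8% | 3.8% |
| 5% | 9/0 | 3.7% | 5.6% |
| 5% | 9/3 | 3.5% | 5.0% |
| 20% | 9/3 | 7.1% | 15.3% |

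At 20% with 6/3 stoppers, dropping gives 9.0%, still below 10%.

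**The case against.** The exceptions formally define a secondary population, while the failure rule is written for the primary endpoint. A patient can properly be a failure in the primary analysis and absent from a secondary one, and randomizing a replacement does not by itself remove anyone from ITT. Exception (1) would have little purpose if exception (2) removed almost every toxicity or progression stopper. Several places also treat the EOT marrow as the endpoint sample. On that usage many early stoppers have a sample, and exception (2) reaches only failed or refused marrows.

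Most of this stands. A reader might infer that the plan has decided to drop treatment failures from its primary analysis; the documents do not support that. What remains is that replacement is tied to the primary endpoint analysis, that the failure rule limits replacement to a different group, and that neither reconciling reading is stated. Even if the EOT marrow counts, an intolerant patient who refuses it or has a dry tap still falls under both rules.

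A reader might also compare 30 patients with failures counted and no replacements against 30 after replacement. That mixes the scoring with the gain from extra patients and overstates the effect.

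**Conclusion.** The conflict is real and textual, and it does not depend on the arithmetic. Its likely effect is modest. Under the assumed stop rates, and with replacements enrolled, the choice of rule moves power by about 0.03 to 0.07 and changes the verdict in roughly 3% to 7% of trials. These sizes rest on reading Table 8-1 as net rates, on replacements who complete, and on 10% to 30% of IRd patients stopping; none of these is in the documents.

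A reader might infer that the planned 10% type I error is broken in general. It is not. At the expected 5% control rate, dropping stoppers keeps the error below 10% in every scenario tried. It passes 10% only at higher control rates combined with strongly unequal stopping.

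The text should still be corrected. The remedy is cheap, and leaving the choice open in an unblinded trial invites decisions made with the arm known.

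**What to change.** Amend Section 8.1.4, and name the population again in Section 8.1.6:

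1. The primary analysis uses the ITT (all-treated) population under the failure rule, apart from patients who decline treatment for reasons unrelated to toxicity or efficacy.
2. Exception (2) applies only to patients who completed 12 cycles but whose 12-month MRD test failed or whose sample is unavailable. They are excluded from the secondary evaluable population only.
3. Patients whose protocol treatment ended early for toxicity, intolerance or progression are evaluable failures and are not replaced.
4. If any such patient has already been replaced, keep that patient in the primary analysis as a failure and report the number by arm.

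The cost is a few sentences. No visit, marrow or test is added, and fewer patients would need replacing.
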